3.5.3 Dabrafenib-Trametinib Dose Modification for Rash

Rash is a frequent AE observed in patients receiving trametinib, dabrafenib, or the combination of both agents. Recommendations for supportive care and guidelines for dose modifications for rash are based on experience with other MEK inhibitors and EGFR inhibitors

The institutional standards for the management of skin-related AEs can differ from these guidelines. In this case, best clinical judgment should be applied and a consultation with the subprotocol Study Chair may be required.

Rev. 8/15

Dabrafenib-Trametinib Supportive care and Dose Modification for Rash		
CTCAE Grade	Adverse Event Management	Action and Dose Modification

Supportive care:
 
Prevention:
 
 
Avoid unnecessary exposure to sunlight
 
Apply broad-spectrum sunscreen (containing titanium dioxide or zinc oxide) with a skin protection factor (SPF) <math>\geq 15</math> at least twice daily.
 
Use thick, alcohol-free emollient cream (e.g., glycerine and cetomacrogol cream) on dry areas of the body at least twice daily.
 
Topical steroids and antibiotics should be applied at least twice daily starting on Day 1 of study treatment, to body areas such as face, chest, and upper back.
 
Use mild-strength topical steroid (hydrocortisone 1% cream) or topical antibiotic (e.g., clindamycin) or oral antibiotics (e.g., doxycycline 100 mg BID, minocycline 100 mg BID)
 
 
Symptom management:
 
 
Pruritic lesions: cool compresses and oral antihistamine therapies
 
Fissuring lesions: Monsel's solution, silver nitrate, or zinc oxide cream
 
Desquamation: thick emollients and mild soap
 
Paronychia: antiseptic bath, local potent corticosteroids in addition to oral antibiotics; if no improvement, consult dermatologist or surgeon
 
Infected lesions: appropriate bacterial/fungal culture-driven systemic or topical antibiotics
 
 
* Rash prophylaxis is recommended for the first 6 weeks of study treatment
 
* Subjects who develop rash/skin toxicities should be seen by a qualified physician and should receive evaluation for symptomatic/supportive care management
		
Grade 1	
 
Initiate prophylactic and symptomatic treatment measures.
 
Use moderate strength topical steroid.
 
Reassess after 2 weeks.
 
	
 
Continue study treatment.
 
If rash does not recover to baseline within 2 weeks despite best supportive care, reduce study treatment with both drugs by one dose level.
 

Grade 2	
 
Initiate prophylactic and symptomatic treatment measures.
 
Use moderate strength topical steroid.
 
Reassess after 2 weeks.
 
	
 
Reduce study treatment with both drugs by one dose level.
 
If rash recovers to <math>\leq</math> grade 1 within 2 weeks, increase dose to previous dose level.
 
If no recovery to <math>\leq</math> grade 1 within 2 weeks, interrupt study treatment until recovery to <math>\leq</math> grade 1.
 
Restart study treatment with both drugs at reduced dose level.
 

Grade <math>\geq 3</math>	
 
Use moderate strength topical steroids PLUS oral methyl-prednisolone dose pack.
 
Consult dermatologist.
 
	
 
Interrupt study treatment until rash recovers to <math>\leq</math> grade 1.
 
Restart study treatment with both drugs reduced by one dose level.
 
If no recovery to <math>\leq</math> grade 2 within 14 days, permanently discontinue study treatment.
 

1. Rash prophylaxis is recommended for the first 6 weeks of study treatment.
 
2. Moderate-strength topical steroids: Hydrocortisone 2.5% cream or fluticasone propionate concentration 0.05% cream.
 
3. Study treatment may be escalated to previous dose level if no rash is evident 4 weeks after restarting study treatment.
		

- 3.5.4 Dabrafenib-Trametinib Dose Modification for palmar-plantar erythrodysesthesia syndrome (PPES)
- Lifestyle modification: avoidance of hot water, traumatic activity, constrictive footwear, or excessive friction on the skin and the use of thick cotton socks and gloves, and shoes with padded insoles
  - Symptomatic treatments: apply moisturizing creams frequently, topical keratolytics (e.g. urea 20-40 % cream, salicylic acid 6%, tazarotene 0.1% cream, fluorouracil 5% cream), clobetasol propionate 0.05% ointment for erythematous areas, topical lidocaine 2%, and / or systemic pain medication such as nonsteroidal anti-inflammatory drugs, codeine, and pregabalin for pain.
  - Dose modification may also be required. – Refer to table for dose modification for non-specific AEs

3.5.5 Dabrafenib-Trametinib Treatment Modification for New Primary/ Recurrent Malignancies

3.5.5.1 Cutaneous SCC and New Primary Melanoma

Dermatologic skin assessments for subjects on treatment should be performed by the treating physician before initiation of dabrafenib, then every 2 months through treatment. For protocols that start after June 2014, it is also recommended that skin exams, per institutional standards, should continue every 2-3 months for 6 months after discontinuation of dabrafenib or initiation of another anti-neoplastic therapy. Report any new primary/recurrent malignancies as SAE through CTEP-AERS if it meets the reporting requirements outlined in Section [3.2.2](#).

Cutaneous Squamous Cell Carcinoma (cuSCC)

Cases of cuSCC (which include those classified as keratoacanthoma [KA] or mixed keratoacanthoma subtype) have been observed in subjects treated with dabrafenib. Approximately 70 % of events occurred within the first 12 weeks of treatment with a median time to onset of 8 weeks.

These should be surgically removed according to institutional practices. Dose modification or interruption of study treatment is not required for cuSCC or KA, however cuSCC should be reported as an SAE (if it meets the reporting requirements outlined in Section [3.2.2](#)). In addition, a biopsy of the lesion should be taken, where possible, and a summary of the results submitted to CTEP through the SAE reporting.

Patients should be instructed to immediately inform their physician if new lesions develop.

### New Primary Melanoma

New primary melanomas have been reported in patients treated with dabrafenib. These were identified primarily within the first 5 months of therapy and did not require treatment modification other than excision. New primary melanoma should be reported as SAE through CTEP-AERS if it meets the reporting requirements outlined in Section [3.2.2](#).

#### 3.5.5.2 Non-Cutaneous Malignancies

*In vitro* experiments have demonstrated paradoxical activation of MAP-kinase signalling in BRAF wild type cells with RAS mutations when exposed to BRAF inhibitors, which may lead to increased risk of non-cutaneous malignancies in patients treated with dabrafenib. Cases of RAS-driven malignancies have been seen with BRAF inhibitors. Patients should be monitored as clinically appropriate.

Permanently discontinue dabrafenib in patients who develop RAS mutation-positive non-cutaneous malignancies. If used in combination with trametinib, trametinib may continue.

Following discontinuation of dabrafenib, monitoring for non-cutaneous secondary/recurrent malignancies should continue for up to 6 months or until initiation of another anti-neoplastic therapy.

New non-cutaneous malignancies should be reported as a SAE if it meets the reporting requirements outlined in Section [3.2.2](#). In addition, a biopsy should be taken, where possible, and a summary of the results submitted to CTEP through the SAE reporting. Testing of these biopsies should include RAS mutation analysis and may include analysis of genomic alterations, which include but not limited to DNA, RNA and protein analysis of these biopsy specimens, and would analyze the biological pathways known to be associated with, and relevant to, BRAF-mutant tumor activation.

#### 3.5.6 Dabrafenib-Trametinib Dose Modification for Hemorrhages

Dabrafenib-Trametinib Treatment Modifications for Hemorrhage	
Grade 3	Hold dabrafenib-trametinib for up to 2 weeks If improved, resume the drugs at one dose reduction If no improvement, permanently discontinue dabrafenib-trametinib
Grade 4	Permanently discontinue dabrafenib or dabrafenib-trametinib

- 
- 3.5.7      Dabrafenib-Trametinib Dose Modification for Pancreatitis
- In the event of abdominal pain or suspected pancreatitis, amylase and lipase laboratory samples should be collected for confirmation of the diagnosis. Patients should be closely monitored when re-starting dabrafenib after an episode of pancreatitis. For changes in treatment, please refer to *Dose Modification for Toxicities Not Specified in Subsequent Sections* Section [3.5.1](#)
- 3.5.8      Dabrafenib-Trametinib Dose Modification for Hyperglycemia
- Hyperglycemia requiring an increase in the dose of, or initiation of insulin or oral therapy can occur with dabrafenib. Monitor serum glucose levels as clinically appropriate during treatment with dabrafenib in subjects with pre-existing diabetes or hyperglycemia. Advise patients to report symptoms of severe hyperglycemia such as excessive thirst or any increase in the volume or frequency of urination. For changes in treatment, please refer to *Dose Modification for Toxicities Not Specified in Subsequent Sections* Section [3.5.1](#)
- 3.5.9      Dabrafenib-Trametinib Dose Modification for Renal Insufficiency
- Cases of renal insufficiency have occurred in patients receiving the combination of dabrafenib and trametinib. Prior to start of study treatment, concomitant medications should be reviewed for the potential risk of inducing nephrotoxicity and modified if clinically possible.

Rev. 8/15

Dabrafenib-Trametinib Dose Modification for Renal Insufficiency		
Serum Creatinine Level	Management Guideline	Action and Dose Modification
Serum creatinine increase > 0.2 mg/dL (18 mcmmol/L) BUT ≤ 0.5 mg/dL (44 mcmmol/L) above baseline	
 
• Recheck serum creatinine within 1 week.
 
• Serum creatinine increase >1 week: contact the subprotocol Study Chair. If elevation persists beyond 4 weeks, recommend evaluation (consider renal biopsy) for etiology; consider nephrology consultation.
 
• If pyrexia is present, treat pyrexia as per guidelines.a
 
	Continue study treatment at the same dose level.
Serum creatinine increase > 0.5 mg/dL (44 mcmmol/L) ABOVE NORMAL OR > 2 mg/dL (> 177 mcmmol/L)	
 
• Monitor serum creatinine ≥ 2-times per week.
 
• Hospitalization may be necessary if serum creatinine cannot be monitored frequently.
 
• If pyrexia is present, treat pyrexia per guidelines.
 
• Consult nephrologist if clinically indicated.
 
• Perform renal biopsy if clinically indicated, for example:               
 
– Renal insufficiency persists despite volume repletion.
 
– Patient has new rash or signs of hypersensitivity (such as elevated eosinophil count).
 
 
 
	
 
• Interrupt study treatment for up to 2 weeks until serum creatinine recovers to baseline.
 
• Restart study treatment.b
 

a NSAIDs can induce renal insufficiency, especially in patients with dehydration; encourage oral fluids or consider IV fluids as clinically indicated. See guidelines for pyrexia Section 3.5.2 . b Investigator may restart at either the same or a reduced dose level. Escalation of study treatment to previous dose level is allowed if another episode of renal insufficiency does not occur after 4 weeks of dose reduction. Consultation with the subprotocol Study Chair is required before restarting study treatment if there is evidence of thrombotic microangiopathy.		

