### 3.5.10 Dabrafenib-Trametinib Dose Modification for Reduced Left Ventricular Ejection Fraction

Decreases of the left ventricular ejection fraction (LVEF) have been observed in patients receiving dabrafenib plus trametinib. Therefore, ECHO/MUGA must be performed in regular intervals outlined in the Study Calendar. The same procedure (either ECHO or MUGA, although ECHO is preferred) should be performed at baseline and at follow-up visit(s).

Rev. 8/15,  
5/16

Dabrafenib - Trametinib Treatment Modification and Management Guidelines for LVEF Decrease		
Clinic	LVEF-drop (%) or CTCAE grade	Dose Modification
Asymptomatic	Absolute decrease of > 10% in LVEF compared to baseline and ejection fraction below the institution's LLN.	
 
Interrupt trametinib. Dabrafenib may continue
 
Repeat ECHO within 2 weeks.a
 
If the LVEF recovers within 4 weeks (defined as LVEF <math>\geq</math> LLN and absolute decrease <math>\leq</math> 10% compared to baseline):               
 
Consult with the subprotocol Study Chair and request approval for restart.
 
Restart trametinib and dabrafenib at reduced doses by one dose level.
 
Repeat ECHO 2, 4, 8, and 12 weeks after re-start; continue in intervals of 12 weeks thereafter.
 
 
 
If LVEF does not recover within 4 weeks:               
 
Consult with cardiologist.
 
Permanently discontinue trametinib. Report as SAE
 
Resumption of dabrafenib may be considered after consultation with the subprotocol Study Chair.
 
Repeat ECHO after 2, 4, 8, 12, and 16 weeks or until resolution.
 
 
 

Symptomatic b	
 
Grade 3: resting LVEF 39-20% or > 20% absolute reduction from baseline
 
Grade 4: Resting LVEF < 20%.
 
	
 
Permanently discontinue trametinib. Report as SAE
 
Hold dabrafenib until LVEF improves. Consult the subprotocol Study Chair for resumption of dabrafenib
 
Consult with cardiologist.
 
Repeat ECHO after 2, 4, 8, 12, and 16 weeks or until resolution.
 

a If ECHO does not show LVEF recovery after 2 weeks, repeat ECHO 2 weeks later. b Symptoms may include: dyspnea, orthopnea, and other signs and symptoms of pulmonary congestion and edema.		

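### Section 3.5.9 sets its two creatinine rows against different references (baseline and an undefined normal), so some values fall in no row and others in both; the LVEF row in 3.5.10 also needs clarifying

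*Protocol*

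**What the plan says.** **Creatinine (section 3.5.9).** The table has two rows.

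- Row 1 runs from "Serum creatinine increase > 0.2 mg/dL (18 mcmmol/L" (closing bracket follows) to "≤ 0.5 mg/dL (44 mcmmol/L) above baseline". Its action is "Continue study treatment at the same dose level".
- Row 2 opens with "Serum creatinine increase > 0.5 mg/dL (44 mcmmol/L" (closing bracket follows). The next words, in capitals, set that rise against normal. A second trigger, joined by OR, is a figure above 2 mg/dL. The action is to interrupt for up to two weeks until creatinine is back at baseline.

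The section does not define normal. Sections 3.5.7 (pancreatitis) and 3.5.8 (hyperglycemia) refer the reader to the general table in 3.5.1. Section 3.5.9 does not, and 3.5.1 is limited by its title to toxicities that the later sections do not specify.

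**LVEF (section 3.5.10, asymptomatic row).** The first action is "Interrupt trametinib. Dabrafenib may continue". If LVEF recovers within four weeks, and after Study Chair approval, the row says "Restart trametinib and dabrafenib at reduced doses by one dose level". If it does not recover, trametinib is stopped for good and "Resumption of dabrafenib may be considered after consultation with the subprotocol Study Chair". No step in this row holds dabrafenib. The symptomatic row of the same table does state a hold.

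**The concern.** The two creatinine rows share a cut of 0.5 mg/dL but measure it from different starting points, so they join only where those points coincide. Elsewhere a patient can have a clear rise that no row covers, or a value that one row says to treat through and the other says to interrupt for. This is a safety rule, and sites reading the same table could handle identical patients differently.

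The protocol treats the toxicity as expected: in section 1.7, increased creatinine is listed in 24% of the 2 mg combination group. Baselines above normal are also foreseen, because footnote B of the study calendar (section 4.1) gives an eligibility calculation for participants whose creatinine exceeds the institutional normal.

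The LVEF question is smaller: what happens to dabrafenib in a patient who, as the row allows, kept taking it.

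**Working it through.** **Inputs from section 3.5.9.** Let B be the patient's baseline and N the value meant by normal, both in mg/dL.

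- Row 1 (continue): above B + 0.2, up to and including B + 0.5.
- Row 2 (interrupt): above N + 0.5, or above 2.0. As a level, this is anything above min(N + 0.5, 2.0).

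**Unit check.** At 88.42 µmol/L per mg/dL, 0.2, 0.5 and 2.0 mg/dL are 17.7, 44.2 and 176.8 µmol/L. The table gives 18, 44 and 177, so the mismatch is not a conversion error.

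**Assumptions.** The protocol gives no value for N. I take N as a laboratory limit of 1.0, 1.2 or 1.3, and choose B for illustration.

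**Gap, when B is below N.** Values above B + 0.5 up to min(N + 0.5, 2.0) are in neither row. While N + 0.5 is at most 2.0, the width is N − B.

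| N (assumed) | B (assumed) | Row 1 ends | Row 2 starts above | In no row |
|---|---|---|---|---|
| 1.0 | 0.6 | 1.1 | 1.5 | above 1.1 to 1.5 |
| 1.2 | 0.6 | 1.1 | 1.7 | above 1.1 to 1.7 |
| 1.3 | 0.6 | 1.1 | 1.8 | above 1.1 to 1.8 |
| 1.2 | 0.8 | 1.3 | 1.7 | above 1.3 to 1.7 |
| 1.2 | 1.0 | 1.5 | 1.7 | above 1.5 to 1.7 |

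**Overlap, when B is above N.** Values above max(B + 0.2, min(N + 0.5, 2.0)) up to B + 0.5 are in both rows.

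| N (assumed) | B (assumed) | Row 1 | Row 2 starts above | In both rows |
|---|---|---|---|---|
| 1.2 | 1.4 | above 1.6 to 1.9 | 1.7 | above 1.7 to 1.9 |
| 1.2 | 1.6 | above 1.8 to 2.1 | 1.7 | above 1.8 to 2.1 (all of row 1) |

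With N + 0.5 at most 2.0, only B = N gives neither gap nor overlap.

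**Sensitivity to the second trigger.** If the 2 mg/dL figure is read as a rise, it would act only above B + 2.0. That is at least 2.6 for the baselines shown, beyond every band in the tables, so none of them changes.

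**LVEF, branch by branch.**

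| Patient during the trametinib hold | LVEF recovers | LVEF does not recover |
|---|---|---|
| Dabrafenib also held | Restart wording fits | Resumption wording fits |
| Dabrafenib continued | Not stated whether it is reduced | Not stated whether consultation is needed to stay on it |

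Section 3.5.14 shows a cleaner pattern: in the visual-change and RPED tables, where trametinib is held and dabrafenib goes on, only trametinib is restarted.

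**The case against.** **The creatinine gap may rest on one word.** Row 2 speaks of an increase, uses the same 0.5 mg/dL cut as row 1, and judges recovery against baseline. One can argue that the rows were meant to meet and that normal is a slip. That is plausible, but the text does not settle it. The table uses both words, and row 2 itself uses baseline for recovery and normal for its trigger. The sponsor has to say which is meant.

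**There is a route for unclear cases.** The guidelines at the start of section 3.5 send questions on how doses should be modified to the CTEP drug monitors, and the LVEF row already involves the Study Chair. This stands: a patient in the gap is not without recourse. It does not make the table consistent.

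**The LVEF row is not a flat contradiction.** A reader might infer that it orders dabrafenib both continued and restarted. It does not. The wording permits continuation, and the later lines read coherently for a patient whose dabrafenib was also held. What remains is silence about the patient who stayed on it.

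**A very high baseline is not by itself a conflict.** A reader might point to a baseline of 1.9 rising by 0.15 to 2.05, which meets row 2 but not row 1. Here the level passes the separate 2 mg/dL trigger and the rise is below row 1's lower bound of 0.2, so the rows do not conflict.

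**Conclusion.** The creatinine table is wrong as written. If normal is a laboratory limit, every patient with a baseline below it has a band with no row. For a baseline of 0.6 and an assumed limit of 1.0 to 1.3 mg/dL, the band is 0.4 to 0.7 mg/dL wide. For a baseline above the limit, the two rows can apply together with opposite actions. The gap and the overlap disappear for all of these patients only if normal is taken to mean baseline, which the document does not say. The numerical bands rest on assumed values of N and B; the mismatch of references does not.

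The LVEF row is a secondary point of clarity.

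Two stronger inferences are not supported.

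- **Number of patients.** Section 1.7 gives renal failure in 7% and cardiac events in 9% of the combination group. Applied to 85 patients these are about 6 (0.07 × 85 = 5.95) and 8 (0.09 × 85 = 7.65). They are overall event rates, not counts of patients in the gap or in the unclear LVEF branch. The cardiac events were all decreased ejection fraction of grade 1 or 2, and nothing shows how many met the row's trigger. The number affected cannot be derived.
- **Effect on efficacy.** Nothing in the document links these cells to the response rate, and no sample size or error rate depends on them.

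Section 1.9 has accrual ending on December 31, 2022, and the number still on treatment is not stated, so few patients may now be exposed. The document carries adverse event lists dated 2025, so it is still being maintained.

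**What to change.** In section 3.5.9, reconcile the two rows to one stated and defined reference, so that every creatinine value above the lowest threshold falls in exactly one row. Also state whether the 2 mg/dL figure is a level or a rise and, if it is a level, which row governs when both apply. Even with a common baseline reference, row 1 would pass 2.0 for any baseline above 1.5 (1.5 + 0.5 = 2.0). The clinical team decides the reference and the precedence; no threshold is proposed here.

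In the asymptomatic row of section 3.5.10, reconcile the lines on dabrafenib so that the row says what applies on recovery and on non-recovery, both to a patient whose dabrafenib was held and to one who stayed on it. That content is also for the clinical team.

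The cost is a wording amendment and notice to sites. No analysis, sample size or data collection changes.

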### 3.5.10 Dabrafenib-Trametinib Dose Modification for Reduced Left Ventricular Ejection Fraction

Decreases of the left ventricular ejection fraction (LVEF) have been observed in patients receiving dabrafenib plus trametinib. Therefore, ECHO/MUGA must be performed in regular intervals outlined in the Study Calendar. The same procedure (either ECHO or MUGA, although ECHO is preferred) should be performed at baseline and at follow-up visit(s).

Rev. 8/15,  
5/16

Dabrafenib - Trametinib Treatment Modification and Management Guidelines for LVEF Decrease		
Clinic	LVEF-drop (%) or CTCAE grade	Dose Modification
Asymptomatic	Absolute decrease of > 10% in LVEF compared to baseline and ejection fraction below the institution's LLN.	
 
Interrupt trametinib. Dabrafenib may continue
 
Repeat ECHO within 2 weeks.a
 
If the LVEF recovers within 4 weeks (defined as LVEF <math>\geq</math> LLN and absolute decrease <math>\leq</math> 10% compared to baseline):               
 
Consult with the subprotocol Study Chair and request approval for restart.
 
Restart trametinib and dabrafenib at reduced doses by one dose level.
 
Repeat ECHO 2, 4, 8, and 12 weeks after re-start; continue in intervals of 12 weeks thereafter.
 
 
 
If LVEF does not recover within 4 weeks:               
 
Consult with cardiologist.
 
Permanently discontinue trametinib. Report as SAE
 
Resumption of dabrafenib may be considered after consultation with the subprotocol Study Chair.
 
Repeat ECHO after 2, 4, 8, 12, and 16 weeks or until resolution.
 
 
 

Symptomatic b	
 
Grade 3: resting LVEF 39-20% or > 20% absolute reduction from baseline
 
Grade 4: Resting LVEF < 20%.
 
	
 
Permanently discontinue trametinib. Report as SAE
 
Hold dabrafenib until LVEF improves. Consult the subprotocol Study Chair for resumption of dabrafenib
 
Consult with cardiologist.
 
Repeat ECHO after 2, 4, 8, 12, and 16 weeks or until resolution.
 

a If ECHO does not show LVEF recovery after 2 weeks, repeat ECHO 2 weeks later. b Symptoms may include: dyspnea, orthopnea, and other signs and symptoms of pulmonary congestion and edema.		

Rev. Add13

